# 5.2 Selection of Comparator

The Infectious Diseases Society of America (IDSA)/American Thoracic Society (ATS) treatment guidelines recommend the use of an anti-pneumococcal fluoroquinolone for hospitalized patients (not in the ICU) with CABP. The guidelines also recommend a fluoroquinolone for outpatients with certain co-morbid conditions, outpatients who have used antimicrobials in the previous few months, and outpatients in regions with high rates of macrolide-resistant *S. pneumonia* regardless of co-morbidities or prior antibiotic use. *The European Society of Clinical Microbiology and Infectious Diseases* also supports the use of fluoroquinolones for outpatient treatment of CABP in areas with increased bacterial resistance rates to tetracyclines and macrolides, as well as for empiric therapy in hospitalized patients with CABP. These guidelines also note that respiratory quinolones may offer advantages over other therapy options for *Legionella* infection and that moxifloxacin has the highest antipneumococcal activity.

Therefore, in order to provide a robust comparison of oral lefamulin to an oral CABP treatment regimen that would be appropriate in multiple regions and in patients with and without co-morbidities, respiratory fluoroquinolones were considered the comparator of choice. Moxifloxacin was chosen over other respiratory fluoroquinolones because the labels of other fluoroquinolones have variable dose and/or treatment durations for CABP depending

on the specifics of approved labels in other countries. In addition, other respiratory fluoroquinolones require adjustment in settings of renal dysfunction which would complicate treatment regimens and create challenges with maintaining the blind.

#### 5.3 Randomization

Qualified subjects will be randomized to receive lefamulin or moxifloxacin in a 1:1 allocation ratio. Randomization may occur following the required assessments and prior to administration of the first dose of study drug.

Randomization will be stratified by PORT Risk Class (Risk Class II vs. III and IV; see Section 6.3), geographic region (US vs. ex-US), and prior (single dose) short-acting antibiotic therapy for CABP vs. none using blocked randomization via IRT. (NOTE: No more than 25 % of randomized subjects will have received a single dose of a short-acting antibiotic). A minimum of 50% of the total number of subjects randomized will have a PORT Risk Class of III or IV.

The randomization schedule will be generated by Nabriva (or designee). Subjects randomized into the study will be assigned the treatment corresponding to the next available number in the respective stratum of the computer-generated randomization schedule. Prior to dosing, study personnel will contact the IRT system to obtain a treatment assignment. Subjects are considered randomized once a randomization number has been assigned regardless of whether the subject receives study drug. Randomized subjects who do not receive study drug or who discontinue participation in the study for any reason will not be replaced.

# 5.4 Study Drug Treatment

The duration of blinded study drug administration will be 7 days.

Subjects randomized to lefamulin will receive oral lefamulin 600 mg q12h for 5 days (10 doses) and oral moxifloxacin placebo q24h for 7 days (7 doses). Subjects randomized to moxifloxacin will receive oral moxifloxacin 400 mg q24h for 7 days (7 doses) and oral lefamulin placebo q12h for 5 days (10 doses).

On Day 1, study personnel will administer the first dose of study drug at the study site to all subjects, as soon as possible after the diagnosis of CABP and completion of all required Day 1 procedures as outlined in Table 1. While subjects are hospitalized, all doses of study drug will be administered by hospital staff or study personnel.

For Outpatients, or in the event a subject is discharged from the hospital during the study drug administration period, an adequate supply of study drug will be dispensed for self-administration at home. Subjects will be provided instructions regarding the dosing schedule. Subjects may self-administer oral study drug at home with the following exception: Study personnel will advise subjects who are Outpatients that they must return to the study site to assess CABP signs and symptoms at  $96 \pm 24$  hours after the first dose of study drug (see Section 6.11). Study personnel will inform Outpatients as to the timing of

this required study site visit. Subjects will be advised not to take their first dose of study drug at home that day, rather to bring their blister packs (used and unused) to the study site where they will take their dose while supervised, so that specific assessments can be performed both prior to and after taking the dose (see Sections 6.4 [ECGs] and 6.14 [PK]).

On Study Day 1, if q12h dosing is not feasible, the 1st and 2nd doses may be administered as close as 8 hours apart, in order to allow 2 doses to be given on Day 1. In this circumstance, the subject's dosing schedule should be adjusted on Day 2 to a regular q12h morning and evening schedule. Subsequently, every effort should be made to maintain a q12h dosing schedule. When this is not possible, it is acceptable to administer doses within 4 hours of the scheduled dosing time (i.e., a minimum of 8 hours between doses).

Study drug should be administered at least 1 hour before a meal or 2 hours after a meal. However, in the event that a subject has taken any of the following – antacids containing aluminum, products containing iron, or multivitamins containing zinc – study drug should be administered 2 hours before or 4 hours after consuming any of these medications. Doses should be administered with approximately 240 mL (8 ounces) of water.

The lot numbers and expiration dates of all study drugs supplied will be recorded.

## 5.5 Blinding

This is a double-blind, double-dummy study.

The study personnel, Sponsor (except as specified), and subject will not know what study drug is being administered.

Study drugs will be provided in blister packs and all study drug administration will utilize a "double-dummy" technique. Details about the double-dummy design and blinding are provided in a Study Procedure Manual. Lefamulin or matching placebo tablets will be provided by the Sponsor. Moxifloxacin will be over encapsulated; matching placebo tablets will also be provided by the Sponsor.

A member(s) of the Sponsor's Clinical Pharmacology group (or designee) will be unblinded to treatment assignment, as appropriate, in order to perform PK/PD assessments. A Data Monitoring Committee (DMC) will review study data by masked treatment group in accordance with the DMC Charter. In addition, as needed to meet regulatory reporting requirements on a country-by-country basis, designated pharmacovigilance personnel may be unblinded to treatment status of individual patients. In this circumstance, and if there are no other concerns, neither the Sponsor nor study personnel will be unblinded to treatment status.

# 5.6 Unblinding of Therapy Assignments

Unblinding of therapy assignment may be requested in an emergency if unblinding is considered necessary for medical management of the subject. In such a case, the Investigator must contact the Sponsor (or designee) and document the reason(s) for the request to unblind.

The Sponsor (or designee) must document any such communication with an Investigator. The IRT system will record the date of any unblinding of individual therapy assignments.

The study will be unblinded for all analyses after the study database is locked, which will occur after the last subject randomized in the study has completed the 30-day post treatment follow-up assessment period.

#### 5.7 Adherence

If subjects are Inpatient, hospital staff or study personnel will administer all doses of study drug and will record the date and time of dosing. In addition, for Outpatients, any doses administered under supervision of study personnel in conjunction with assessments/procedures (e.g., PK sampling, ECGs), study personnel will also record the date and time of those doses.

Outpatient subjects will be instructed to bring all used and unused blister packs to each study visit so that drug accountability can be reviewed by study personnel. Study personnel will collect all blister packs (empty or containing unused study drug) at the EOT visit (see Section 8.3.3). The total number of pills dispensed on Day 1 and returned at the EOT visit will be recorded in the eCRF.

## 5.8 Occupational Safety

Lefamulin and moxifloxacin being used in this study are not expected to pose a significant occupational safety risk to study personnel under normal conditions of use and administration.

A Material Safety Data Sheet describing occupational hazards and recommended handling precautions either will be provided to the Investigator, where this is required by local laws, or is available upon request from Nabriva Therapeutics AG.

#### 6 STUDY ASSESSMENTS AND PROCEDURES

A schedule of study procedures is presented in Table 1. Subjects meeting the eligibility criteria listed in Section 4 may be enrolled in the study after the nature and purpose of the protocol have been explained and written informed consent to participate has been voluntarily given by the subject or the subject's legally authorized representative in accordance with local regulations.

Study personnel must complete all screening procedures after informed consent is signed and prior to the first dose of study drug. Note: Assessments performed as part of routine standard of care prior to consent (e.g., chest X-ray, blood culture) may be used to satisfy study screening requirements; however, no study specific procedures may be performed prior to informed consent.

During the Study Drug Administration Period, the first dose of study drug is counted as 0 Hour on Day 1. The Investigator should make every effort to perform procedures at the

scheduled times and to record the actual time of the procedures, where appropriate, in the subject's eCRF.

For subjects who are screened (i.e., those with signed written informed consent) but who are not randomized, the reason for screening failure will be recorded.

## 6.1 Inpatient and Outpatient Assessments

As shown in the Schedule of Assessments and Procedures (see Table 1), the timing of assessments and procedures during the Study Drug Administration Period (Days 1-7) may differ between subjects who are Inpatient versus Outpatient.

Hospitalization is not a requirement for this study (i.e., subjects do not need to be admitted to the hospital to participate and those who are admitted may be discharged at any time at the discretion of the investigator).

While Inpatient, all assessments and procedures (including daily study drug administration) will be conducted at the study site/hospital in accordance with the schedule shown in Table 1 (Screening/Baseline through LFU). While Outpatient, the study site must contact the subjects by telephone daily to assess CABP signs and symptoms, assess for the presence of AEs, and determine changes in concomitant medications (see Sections 6.11, 7, and 6.8.2).

All subjects, including Outpatients, must be evaluated by at the investigational site by study personnel at the following time points/visits: Screening/Baseline; Day 1;  $96 \pm 24$  hours after the first dose of study drug; EOT; TOC; and LFU (see Table 1).

## 6.1.1 Outpatient Visit for ECR Assessment and Other Site Procedures

Outpatients must return to the site for a face-to-face visit with study personnel  $96 \pm 24$  hours (i.e., 72 to 120 hours) after the first dose of study drug. Study personnel will inform Outpatients as to the timing of this required study site visit in the course of the daily telephone contacts.

The purpose of this site visit is to assess CABP signs and symptoms which will be used to programmatically determine the ECR, as well as to perform other procedures that cannot be done by telephone (i.e., ECG, blood samples for PK analysis, blood samples for safety assessments, vital signs, and physical examination).

ECGs and blood samples for PK analysis must be performed within specified time windows before and after study drug administration. Therefore, it is **critical** that the subject be instructed to not take their first dose of study drug at home that day, rather to bring all their blister packs (used and unused) to the study site. The dose associated with the outpatient visit for ECR assessment and other site procedures will be taken under supervision of study personnel. In addition, as discussed in Sections 5.4 and 6.17, study personnel will remind subjects regarding adherence to the food and supplement restrictions when scheduling this visit.

## 6.2 Medical/Surgical History and Physical Examination

A medical and surgical history will be taken at Screening. All medical history findings that have been present or active within the 5 years prior to enrollment will be entered into the eCRF regardless of clinical relevance or presence at study start. Medical history findings that have not been present within the 5 years prior to enrollment will be recorded if deemed clinically relevant by the Investigator to the conduct of the study. The medical history should include drug allergy history, past and present smoking status, influenza virus and pneumococcal vaccination history, as well as the presence of influenza virus infection during the current illness.

A complete physical examination will be performed by the Investigator at Screening. At the time points specified in Table 1, subsequent directed physical examinations will be performed according to standard institutional practices and must be documented in source documents.

Body weight and height will be measured at Screening only.

## 6.3 PORT Risk Class Assessment

Study personnel will determine the subject's PORT Score (Table 2) and subsequent PORT Risk Class (Table 3) at Screening only.

Table 2. PORT Score Determination

Patient Characteristic	Point Assignment
Age	1 point for each year of age
Female	−10 if yes
Neoplastic disease history	+30 if yes
Liver disease	+20 if yes
Congestive heart failure	+10 if yes
Cerebrovascular disease	+10 if yes
Renal disease	+10 if yes
Altered mental status	+20 if yes
Respiratory rate ≥ 30 breaths/min	+20 if yes
Systolic blood pressure < 90 mmHg	+20 if yes
Temperature $< 35  ^{\circ}\text{C} (95  ^{\circ}\text{F}) \text{ or } \ge 40  ^{\circ}\text{C} (104  ^{\circ}\text{F})$	+15 if yes
Pulse ≥125 beats/min	+10 if yes
pH <7.35 (from ABG)	+30 if yes
	(+0 if ABG not obtained)
Blood urea nitrogen > 30 mg/dL (Urea > 11 mmol/L)	+20 if yes
Sodium < 130 mmol/L	+20 if yes
Glucose $\geq 250 \text{ mg/dL} (\geq 14 \text{ mmol/L})$	+10 if yes
Hematocrit < 30 %	+10 if yes
Partial pressure of arterial $O_2 < 60 \text{ mmHg}$ (from ABG if medically indicated) or $O_2$ saturation $< 90 \%$ (by pulse oximetry)	+10 if yes
Pleural effusion on radiograph	+10 if yes
PORT SCORE	Sum of Applicable Numbers Above

Table 3. PORT Risk Class Determination

PORT Risk Class	PORT Score
I (Ineligible for Study)	0-50
II	51-70
III	71-90
IV	91-130
V (Ineligible for Study)	> 130

## 6.4 Electrocardiograms

Triplicate 12-lead ECGs will be performed within a 5-minute interval at time points specified in Table 1. The subject should be stabilized in a supine position for 5 minutes before recording the ECG. ECG recordings should allow a full assessment of QT intervals. Machine-read values for QTc/QTcF will be evaluated for determination of eligibility at Screening. If the quality of the ECG is insufficient then it must be repeated. All ECG data must be reviewed by the Investigator or designee and any findings of clinical significance found following Screening will be recorded as AEs in the eCRF. In addition, advice may be sought from appropriate cardiologists, if necessary. ECGs will be made available to the Sponsor for review and will be sent to a Cardiac Core Laboratory for further evaluation.

If Screening and Day 1 are on the same day, the Screening ECG can serve as the Day 1 ECG prior to the first dose of study drug; an additional ECG must be performed 1-3 hours after administration of first dose.

On Day 4 (Inpatients) or  $96 \pm 24$  hour post first dose (Outpatients), ECGs in triplicate are required prior to the first dose of study drug and again within 1-3 hours after the first dose of study drug. Thus, Outpatients will be advised not to take their first dose of study drug at home that day, rather to bring their blister packs (used and unused) to the study site where they will take their dose while supervised so that the ECGs can be performed both prior to and after taking the dose.

As discussed in detail in Section 6.18.3, if at any time the subject demonstrates an average QTcF value > 500 ms (mean of 3 ECGs at any time point), or an average QTcF value > 480 ms with a concurrent increase in average QTcF value of > 60 ms (mean of 3 post-dose ECGs compared to mean pre-dose ECG's taken on that day) study drug will be discontinued.

# 6.5 Vital Signs and Oxygen Saturation

Vital signs (HR, BP, respiratory rate and body temperature) and oxygen saturation will be recorded at time points specified in Table 1. Blood pressure and heart rate assessments will be performed according to standard practice at the clinical sites. Vital signs associated with the highest temperature after the first dose of study drug will be recorded in the eCRF.

In addition, if the subject is receiving supplemental oxygen therapy, the amount given will be recorded in the eCRF.

All subjects will have vital signs and O2 saturation evaluated at Screening/Baseline and Day 1. If screening/baseline and Day 1 occur on the same calendar day, vital signs and O2 saturation do not need to be repeated. All subjects will also have assessments at EOT and TOC; at LFU, vital signs should be performed if medically indicated. If EOT and the last day of study drug are the same day, vital signs do not need to be repeated, they may be recorded once on that day (i.e., as part of the EOT assessment).

For Inpatients, in addition to the above time points, vital signs and O2 saturation will be measured daily and recorded. If multiple vital signs are taken on a study day, the highest

temperature and the vital signs associated with that high temperature will be recorded. For Outpatients, in addition to the above time points, vital signs and saturation will be measured at the study visit scheduled  $96 \pm 24$  hour after the first dose of study drug (see Section 6.1.1).

Vital signs measurements are to be repeated if clinically significant changes or machine errors occur. Out of range BP and HR will be repeated at the Investigator's discretion. Semi-supine BP and HR will be measured more frequently if warranted by the clinical condition of the subject.

## 6.6 Chest X-Ray or CT Scan

Chest x-ray will be performed at the Screening/Baseline visit as specified in Table 1 and evaluated by the Investigator (or designee) to qualify a subject for enrollment; however, the imaging study must also be interpreted by a radiologist. If a chest computed tomography scan has been performed within 48 hours of enrollment and demonstrates findings consistent with pneumonia, it can be used in place of a chest x-ray. The test type and date and the Investigator's and radiologist's reading/interpretation will be recorded in the eCRF.

## 6.7 Arterial Blood Gases

Study sites are not required to measure arterial blood gases (PaO2, PaCO2) or pH. However, if these data are available, they should be recorded in the eCRF.

## 6.8 Prior and Concomitant Medications

Prior and concomitant medications that will be recorded include prescription medications, dietary supplements/vitamins, and over-the-counter medications. Topical medications will be recorded only if used as treatment for an AE. The minimum requirement is that drug name, indication and the stop and start dates of administration are to be recorded. For the following agents, the drug dose, route and frequency will also be collected in the eCRF:

- Systemic antibacterial agents
- Corticosteroids

Additionally, for systemic antibacterial agents start time and stop time will be recorded.

#### 6.8.1 Prior Medications

A medication history will be taken at Screening. All medications taken within 1 week prior to Day 1 will be entered into the eCRF.

#### 6.8.2 Concomitant Medication

All concomitant medications taken during the study will be recorded in the subject's eCRF.

In the case that additional antibiotic treatment is required for the current episode of CABP, the subject's study drug will be discontinued and they will be considered to have an IACR of

Failure; however, subjects will continue to be followed for safety as detailed in Section 6.18.1.

Other systemic antibacterial agents that are potentially effective against pathogens associated with CABP should not be administered during the study except in the case of CABP treatment failure or when medically necessary for treatment of a concomitant infection. The following antibacterial agents are permitted:

- Anti-tuberculosis drugs isoniazid, ethambutol and pyrazinamide
- Cinoxacin
- Dapsone
- Enoxacin
- Fidaxomicin
- Methenamine Mandelate
- Metronidazole
- Naladixic Acid
- Nitrofurantoin
- Norfloxacin
- Oral Vancomycin

Although all drugs that are metabolized by CYP3A4 are not prohibited, they should only be used when necessary and with appropriate subject monitoring. *In vitro* studies demonstrated that lefamulin may inhibit the metabolism of substrates of CYP3A4; however, results obtained from Phase 1 drug interaction studies performed demonstrate that lefamulin has a marginal effect on CYP3A4 inhibition in humans and no change in lefamulin's dose is required. In addition, all drugs that are P-glycoprotein substrates are not prohibited; however, they should only be used when necessary and with appropriate subject monitoring. A list of drugs that are CYP3A4 substrates and P-glycoprotein substrates is provided in Appendix 3.

Close monitoring is recommended in subjects who require medication that can reduce potassium levels (e.g., loop and thiazide-type diuretics, laxatives and enemas [high doses], corticosteroids, amphotericin B) or medication that is associated with clinically significant bradycardia.

#### 6.9 Prohibited Medications

The following medications are prohibited:

- Prior (within 72 hours before randomization) oral or IV antibacterials for CABP.
  - NOTE: Up to 25 % of subjects may have a single dose of a short-acting antibiotic for the current episode of CABP within 72 hours of randomization.

- EXCEPTION: A subject who has received > 48 hours of prior systemic antibacterial therapy for the current episode of CABP with unequivocal evidence of treatment failure (i.e., worsening signs and symptoms) and the isolation of an organism from blood or respiratory tract that is resistant to the prior systemic antibacterial therapy, provided the organism is not resistant to fluoroquinolones.
- Agents that prolong the QT interval (see Appendix 5)
- Systemic corticosteroids at a dose  $\geq$  20 mg per day (prednisone equivalent)
- Anti-epilepsy or seizure medication
- Strong p-glycoprotein inhibitors (see Appendix 4) [NOTE: The use of contraceptives containing progesterone is not permitted.]
- Strong CYP3A inhibitors or inducers (see Appendix 4)

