The effect of lefamulin on the cardiac conduction parameters of RR, QT, and QTcF has been closely monitored in all clinical studies. A  $C_{max}$ -dependent, predictable, and reproducible prolongation of the QT/QTcF interval has been observed. A thorough analysis of ECGs in the Phase 2 study demonstrated that lefamulin prolonged cardiac depolarization and repolarization duration, but otherwise had a similar cardiac safety profile to that of vancomycin based on evaluations of 12-lead ECGs. Therefore, it is expected that lefamulin will not produce large effects on cardiac de- and repolarization duration. No drug-related cardiac AE — such as increase in ectopic ventricular activity or other cardiac arrhythmia — or clinically relevant ECG findings was reported during the conduct of the studies. None of the protocol-defined stopping criteria (i.e., QTcF > 500 ms and  $\Delta$ QTcF > 60 ms) was reached in any clinical study.

In summary, the results of the Phase 2 study provide the first proof of concept for the systemic use of a pleuromutilin antibiotic in subjects and support the further clinical evaluation of lefamulin for therapy of serious infections. Pharmacokinetic/pharmacodynamic analyses suggest that lefamulin 150 mg IV q12h is an efficacious dosing regimen for Phase 3 studies. Based on available safety data, lefamulin 150 mg IV q12h produced therapeutic exposures and demonstrated an acceptable benefit/risk profile for the treatment of infected subjects. Oral doses of 600 mg lefamulin produced similar systemic exposures to 150 mg IV with a similar benefit/risk profile and were well tolerated in Phase 1 studies with no signs or symptoms of clinical concern.

This is the first Phase 3 study to be conducted in subjects with CABP to be treated only with oral administration of pleuromutilin antibiotic. Subjects will receive treatment with either lefamulin or moxifloxacin, a standard of care treatment for CABP.

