- Receipt within 7 days before enrollment of Class IA or Class III anti-arrhythmic medication or, in the opinion of the Investigator, subject may require such medication during the study. (Class 1A: Quinidine, Procainamide, Disopyramide; Class III: Amiodarone, Dofetilide, Ibutilide, Sotalol)
- Receipt within 7 days before enrollment of medication that has the potential of prolonging the QT interval or, in the opinion of the Investigator, subject may require such medication during the study (see Appendix 5).
- 8. Be receiving a strong p-glycoprotein inhibitor or a strong CYP3A inducer or inhibitor (see Appendix 4).
- 9. Have a history of tendon disease/disorder, myasthenia gravis, or known or suspected central nervous system (CNS) disorders (severe cerebrovascular arteriosclerosis, epilepsy, or other risk factors that may predispose to seizures).
- 10. Have a history of any hypersensitivity or allergic reaction to any fluoroquinolone, or any drug in the pleuromutilin class (i.e., retapamulin).
- 11. Have severely impaired renal function, defined as estimated creatinine clearance (CrCl) ≤30 mL/min as calculated by the Cockcroft-Gault formula.
- 12. Have evidence of significant hepatic, hematologic, or immunologic disease including any of the following:
  - Known acute hepatitis, including acute viral hepatitis.
  - Aspartate aminotransferase (AST) or alanine aminotransferase (ALT) level > 5 times the upper limit of normal (ULN),
  - Total bilirubin > 3 times the ULN (unless known Gilbert's disease).
  - Aspartate aminotransferase (AST) or alanine aminotransferase (ALT) level > 3 times the upper limit of normal (ULN) and total bilirubin > 2 times the ULN.
  - History of cirrhosis of the liver.
  - Manifestation of end-stage liver disease, such as ascites or hepatic encephalopathy.
  - Current or anticipated neutropenia (<500 neutrophils/mm^3).
  - Thrombocytopenia (<50,000 platelets/mm^3).
  - Known infection with human immunodeficiency virus and a CD4 count < 200/mm^3.
- 13. Have known severe immunosuppression, including but not limited to receipt of corticosteroid therapy (≥20 mg of prednisone/day or equivalent for >4 weeks) within the previous 8 weeks; solid organ or bone marrow transplantation within the previous 12 months; or currently receiving cytotoxic chemotherapy.

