# Appendix 3 Closely Monitored CYP3A4 Substrates and P-Glycoprotein Substrates (excluding strong CY3A inducers and inhibitors and excluding strong P-glycoprotein inhibitors)

Closely Monitored CYP3A4 Substrates		
Alfentanyl	Domperidone	Pimozide
Alprazolam	Eplerenone	Progesterone
Amiodipine	Estradiol	Propranolol
Aprepitant	Fentanyl	Quetiapine
Aripiprazole	Finasteride	Quinine
Astemizole	Gleevec	Reserpine
Buspirone	Haloperidol	Salmeterol
Cafergot	Hydrocortisone	Sildenafil
Caffeine	Lercanidipine	Sirolimus
Chlorpheniramine	Lidocaine	Terfenadine
Cilostazol	Methadone	Testosterone
Cocaine	Midazolam	Trazodone
Codeine	Nateglinide	Triazolam
Dapsone	Nifedipine	Zaleplon
Dexamethasone	Nisoldipine	Ziprasidone
Dextromethorphan	Nitrendipine	Zolpidem
Docetaxel	Ondansetron	

Closely Monitored P-Glycoprotein Substrates		
Apixaban	Fexofenadine	Ranitidine
Carvedilol	Fosamprenavir	Rivaroxaban
Cimetidine	Ivermectin	Saxagliptin
Colchicine	Ledipasvir	Silodosin
Dabigatran	Loperamide	Sitagliptin
Daclatasvir	Losartan	Sofosbuvir
Dasabuvir	Maraviroc	Tetracycline
Dexamethasone	Methylprednisolone	Tipranavir
Digoxin	Methotrexate	Tolvaptan
Domperidone	Morphine	Umeclidinium
Edoxaban	Ombitasvir	Vecuronium
Empagliflozin	Paliperidone	Vilanterol
Estradiol	Paritaprevir	
Ezetimibe	Prazosin	

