# Appendix 5 Drugs That Prolong QT

Anticonvulsants	Fosphenytoin; Felbamate
Antihistamines	Azelastine, Clemastine
Anti-infectives	Amantadine, Clarithromycin, Chloroquine, Foscarnet, Erythromycin, Halofantrine, Mefloquine, Pentamidine, Sparfloxacin, Quinine, Trimethoprim-Sulfamethoxazole, Ketoconazole
Antineoplastics	Tamoxifen
Cardiovascular	
Antiarrhythmics	Amiodarone, Bretylium, Disopyramide, Flecainide, Ibutilide, Procainamide, Quinidine, Sotalol, Dofetilide
Calcium Channel Blockers	Bepridil, Israpidine, Nicardipine
Diuretics	Indapamide, Moexipril/ hydrochlorothiazide
Hormones	Octreotide, Vasopressin
Immunosuppressives	Tacrolimus
Migraine: Serotonin Receptor Agonists	Zolmitriptan, Naratriptan, Sumatriptan
Muscle Relaxants	Tizanidine
Narcotic Detoxification	Levomethadyl
Psycotherapeutics	
Antidepressants	Amitriptyline, Desipramine, Fluoxetine, Imipramine, Venlafaxine
Antipsychotics	Chlorpromazine, Haloperidol, Pimozide, Quetiapine, Risperidone, Thioridazine
Antianxiety	Doxepin
Antimanic	Lithium
Respiratory (Sympathomimetics)	Salmeterol
Sedative/Hypnotics	Chloral hydrate

Note: List not exhaustive

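### Appendix 3, the list of CYP3A4 substrates usable with monitoring, names five drugs that Section 6.9 and Appendix 5 prohibit as QT-prolonging

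*Protocol*

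**What the plan says.** Four parts of the protocol bear on this.

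- **Section 6.8.2 (Concomitant Medication)** sets the rule for CYP3A4 substrates: "Although all drugs that are metabolized by CYP3A4 are not prohibited, they should only be used when necessary and with appropriate subject monitoring". It applies the same rule to P-glycoprotein substrates and then gives the source list: "A list of drugs that are CYP3A4 substrates and P-glycoprotein substrates is provided in Appendix 3".
- **Appendix 3** heads its two tables as closely monitored substrates. Its title names what has been left out: "excluding strong CY3A inducers and inhibitors and excluding strong P-glycoprotein inhibitors". QT-prolonging drugs are not mentioned.
- **Section 6.9 (Prohibited Medications)** lists "Agents that prolong the QT interval (see Appendix 5") among the prohibited medications, with no exception attached.
- **Appendix 5** names the QT-prolonging drugs by class. Its antipsychotic row, for example, reads "Chlorpromazine, Haloperidol, Pimozide, Quetiapine, Risperidone, Thioridazine". It closes with "Note: List not exhaustive".

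Eligibility is handled separately. Exclusion criterion 7 in Section 4.2 bars QT-prolonging medication taken within 7 days before enrollment, and also bars a subject when, "in the opinion of the Investigator, subject may require such medication during the study (see Appendix 5").

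**The concern.** The protocol gives two different instructions for the same drug. Through Section 6.8.2, Appendix 3 tells a site to use it only if needed and to monitor. Through Section 6.9, Appendix 5 tells the site not to use it. Because the Appendix 3 title says that certain prohibited classes have been removed, a reader can reasonably assume that whatever remains on the list is allowed with care.

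What is at stake is subject safety. Section 1.5.3 says of lefamulin that a Cmax-dependent, "predictable, and reproducible prolongation of the QT/QTcF interval has been observed". Adding a second QT-prolonging drug is what Section 6.9 is meant to prevent. The exposed situation is an unanticipated need that arises after randomization. Exclusion criterion 7 does not reach that case, and it is when a site would turn to Section 6.8.2 and Appendix 3.

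**Working it through.** No sample size, power or alpha figure is involved. The check compares the lists by drug name.

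**Inputs**

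- Appendix 3, CYP3A4 substrates: three columns of 17 + 17 + 16 = 50 entries.
- Appendix 3, P-glycoprotein substrates: three columns of 14 + 14 + 12 = 40 entries.
- Appendix 5: 54 entries, counting each combination product once.
- Appendix 4: the prohibited strong P-glycoprotein inhibitors and strong CYP3A inhibitors and inducers.

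**Step 1: Appendix 3 CYP3A4 list against Appendix 5.** The overlap is five names, 5/50 = 10% of the entries.

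| Drug | Appendix 3 | Appendix 5 class | In Appendix 4? |
|---|---|---|---|
| Haloperidol | CYP3A4 substrate | Antipsychotic | No |
| Pimozide | CYP3A4 substrate | Antipsychotic | No |
| Quetiapine | CYP3A4 substrate | Antipsychotic | No |
| Quinine | CYP3A4 substrate | Anti-infective | No |
| Salmeterol | CYP3A4 substrate | Respiratory sympathomimetic | No |

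**Step 2: Appendix 3 P-glycoprotein list against Appendix 5.** The overlap is 0 of 40.

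**Step 3: does the carve-out in the Appendix 3 title remove any of the five?** It removes the Appendix 4 classes only. None of the five is in Appendix 4, so it removes 0 of 5.

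**Step 4: does Appendix 3 follow its own carve-out?** Not fully. Carvedilol, methadone, progesterone and reserpine are in Appendix 3 and are also prohibited in Appendix 4 as strong P-glycoprotein inhibitors. None of these four is in Appendix 5, so this is a separate slip, and correcting it would leave the five in place.

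**Step 5: which text governs?** Section 6.9 is explicit and unconditional. Amendment 2 resolved a conflict of the same kind, between an allowance for oral contraceptives and the Appendix 4 prohibition of progesterone, in favour of the prohibition. Both point to the five drugs being prohibited. Neither Section 6.8.2 nor Appendix 3 says so.

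**Step 6: would the ECG safeguards catch an error?** Only in part.

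- ECGs are scheduled at Screening, Day 1 and Day 4 (96 ± 24 hours for outpatients), while blinded dosing runs through Day 7. A drug started after the Day 4 ECG meets no later scheduled ECG.
- The stopping rule at QTcF above 480 ms (Section 6.18.3) also requires a rise of more than 60 ms over the same day's pre-dose ECGs. Prolongation from a co-medication that is already present pre-dose would be part of that reference.
- The rule at QTcF above 500 ms has no such condition, but it too acts only after exposure.

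**The case against.** The strongest case against the point is that no rule contradicts another. Section 6.8.2 can be read as saying only that CYP3A4 metabolism does not by itself bar a drug. On that reading Appendix 3 is a pharmacological list, not a list of permitted drugs; where the protocol grants permission, as it does for certain antibacterials in the same section, it says so. A drug can be a CYP3A4 substrate and also be prohibited on another ground, and Section 6.9 follows immediately. Sites must already apply Appendix 5 at screening under exclusion criterion 7, so an error needs an unanticipated prescription during a 7-day course at a site that overlooks both Section 6.9 and the appendix it used at enrollment. Section 1.5.3 also reports no drug-related cardiac adverse events and no subject reaching a QTcF stopping criterion in the completed studies, and it expects no large effect.

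Much of this stands. The prohibition is the governing rule, eligibility is not in doubt, and the residual scenario is narrow. What does not follow is that the lists are sound. Appendix 3 is headed as a list for close monitoring, Section 6.8.2 ties it to use with monitoring, and its title implies that prohibited drugs were screened out. For five drugs that is the wrong instruction, and nothing in Section 6.8.2 or Appendix 3 sends the reader on to Appendix 5.

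It is also fair to say that deleting five names while leaving the four Appendix 4 overlaps would be uneven. The precedence sentence proposed below covers those four as well.

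**Conclusion.** The inconsistency is real and wrong as written. Five of the 50 CYP3A4 entries in Appendix 3 are prohibited under Section 6.9 and Appendix 5, and the carve-out in the Appendix 3 title removes none of them. The error lies in Appendix 3 and Section 6.8.2, not in the prohibition.

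The counts are of list entries, not subjects. The documents give no figure for how often any of these drugs would be needed on study, so the number of subjects at risk cannot be stated. Treatment is randomized and blinded, so no bias between arms is claimed; any effect on the QTcF tables is unknown. Sample size, power and the primary analysis do not change. The correction should be made because it concerns a safety prohibition for a drug that reproducibly prolongs QTcF and costs almost nothing, but the trial's conclusion does not depend on it.

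**What to change.** 1. Delete haloperidol, pimozide, quetiapine, quinine and salmeterol from Appendix 3. They remain prohibited under Section 6.9 and Appendix 5.
2. Extend the Appendix 3 title with: *and excluding QT-prolonging agents (Appendix 5)*.
3. In Section 6.8.2, after the reference to Appendix 3, add: *Any drug in Appendix 4, and any QT-prolonging agent (Appendix 5), remains prohibited under Section 6.9 even if it is a CYP3A4 or P-glycoprotein substrate.*

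The sentence in item 3 is needed as well as the deletions because Appendix 5 is not a complete list: an unlisted QT-prolonging CYP3A4 substrate would otherwise raise the same question. It also settles the status of carvedilol, methadone, progesterone and reserpine, which could be removed from Appendix 3 at the same time.

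The cost is five deletions, one title phrase and one sentence, made in the next amendment or sent to sites by memo in the meantime. Nothing in the sample size or the analysis changes.
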